2 ELIGIBILITY ASSESSMENT AND ENROLLMENT

2.1 ELIGIBILITY CRITERIA

2.1.1 Inclusion Criteria

- 2.1.1.1 Patients with multiple myeloma treated with induction therapy or re-induction therapy, who at the time of study enrollment have documented evidence of stable disease response or better according to International Myeloma Workshop Consensus Panel as provided in Section 6.2. The response assessment must occur at least 4 weeks after completion of their last treatment.
- 2.1.1.2 Age \geq 18 years. Because no dosing or adverse event data are currently available on the use of lenalidomide in patients $<$ 18 years of age, children are excluded from this study, but may be eligible for future pediatric trials.
- 2.1.1.3 ECOG performance status \leq 2 (see Appendix A).
- 2.1.1.4 Patient must have adequate hematologic, renal, hepatic, and cardiac function as defined by:
 - Absolute neutrophil count \geq 1.0K / μ L independent of growth factor support
 - Platelets \geq 75K/ μ L
 - Hemoglobin \geq 8 g/dL (transfusions are permissible)
 - Calculated creatinine (CrCl) clearance of greater than or equal to 40 mL/min. using the Cockcroft-Gault method (see Appendix E). If the calculated CrCl based on Cockcroft-Gault method is $<$ 40 mL/min, patient will have a 24 hr urine collection to measure CrCl. The measured CrCl must also be \geq 40 ml/min.
 - Total bilirubin \leq 1.5 mg/dL, AST (SGOT) and ALT (SGPT) \leq 3 x ULN
- 2.1.1.5 Females of childbearing potential (FCBP) must agree to use two effective forms of contraception simultaneously or to practice complete abstinence from heterosexual intercourse during the following time periods related to this study: 1) for at least 28 days before starting study drug; 2) while participating in the study; and 3) for at least

28 days after discontinuation from the study. The two methods of effective contraception must include one highly effective method (i.e. intrauterine device (IUD), hormonal [birth control pills, injections, or implants], tubal ligation, partner's vasectomy) and one additional effective (barrier) method (i.e. latex condom, diaphragm, cervical cap). FCBP must be referred to a qualified provider of contraceptive methods if needed.

- 2.1.1.6 A FCBP is defined as a sexually mature woman who: 1) has not undergone a hysterectomy or bilateral oophorectomy; or 2) has not been naturally postmenopausal for at least 24 consecutive months (i.e., has had menses at any time in the preceding 24 consecutive months).
- 2.1.1.7 A FCBP must have two negative serum or urine pregnancy tests prior to starting study drug. The first pregnancy test must be performed within 10-14 days prior to the start of study drug and the second pregnancy test must be performed within 24 hours prior to prescribing the study drug. The prescriptions of study drug must be filled within 7 days.
- 2.1.1.8 Male patients must agree to use a latex condom during sexual contact with FCBP while participating in the study and for at least 28 days following discontinuation from the study even if he has undergone a successful vasectomy.
- 2.1.1.9 Patient must be able to take aspirin (81 or 325 mg) daily as prophylactic anticoagulation. Patients intolerant to ASA may use warfarin or low molecular weight heparin.
- 2.1.1.10 Patient must understand and voluntarily sign an informed consent form, with the understanding that the patient may withdraw consent at any time without prejudice to future medical care.

2.1.2 Exclusion Criteria

- 2.1.2.1 Patients with progressive or refractory MM, as defined by International Myeloma Workshop Consensus Panel criteria provided in section [6.2](#)
- 2.1.2.2 Refractory to lenalidomide in the most recent line of therapy, as defined by the International Myeloma Consensus Panel criteria [47]- as failure to achieve minimal response or development of progressive disease while on lenalidomide or within 30 days of lenalidomide therapy
- 2.1.2.3 Patients who are receiving any other investigational agents with the intent to treat myeloma. Permitted concurrent therapies include:
 - Bisphosphonates
 - Radiotherapy to single stable disease site
- 2.1.2.4 Plasma cell leukemia
- 2.1.2.5 Pregnant or lactating females. Because there is a potential risk for adverse events to nursing infants secondary to treatment of the mother with lenalidomide, lactating females must agree not to breast feed while taking lenalidomide.
- 2.1.2.6 Uncontrolled hypertension or diabetes
- 2.1.2.7 Active hepatitis B or C infection

Abbreviated Title: Revlimid maintenance for MM

Version Date: 01/06/2017

- 2.1.2.8 Diagnosed or treated for another malignancy within 3 years prior to study enrollment, with the exception of complete resection of non-melanoma skin cancer, or an in situ malignancy.
- 2.1.2.9 Previous diagnosis of another malignancy with any evidence of residual disease.
- 2.1.2.10 Patients seropositive for the human immunodeficiency virus (HIV), and/or those who are taking anti-retroviral treatment for HIV/AIDS
- 2.1.2.11 Prior organ transplant requiring immunosuppressive therapy
- 2.1.2.12 Prior allogeneic stem cell transplant
- 2.1.2.13 Patients requiring continuous, systemic immunosuppressive therapy
- 2.1.2.14 Patients with myocardial infarction within 6 months prior to enrollment, New York Heart Association (NYHA) Class III or IV heart failure, uncontrolled angina, severe uncontrolled cardiac arrhythmias, or electrocardiographic evidence of acute ischemia
- 2.1.2.15 Patients with conditions that would prevent absorption of the study drug
- 2.1.2.16 Uncontrolled intercurrent illness including but not limited to uncontrolled infection or psychiatric illness/social situations that would compromise compliance with study requirements
- 2.1.2.17 Significant neuropathy \geq Grade 3 at baseline
- 2.1.2.18 Contraindication to concomitant anticoagulation prophylaxis
- 2.1.2.19 Major surgery within 1 month prior to enrollment
- 2.1.2.20 Patients who were previously exposed and who developed severe adverse events, hypersensitivity or desquamating rash to either thalidomide or lenalidomide

2.1.3 Recruitment Strategies

- 1) Patients with newly diagnosed MM who have completed induction treatment with CRd on trial 11-C-0221.
- 2) Patients with relapsed multiple myeloma after completing treatment on expanded access CRd trial 12-C-0043 or other appropriate NCI trials.
- 3) Other participant sources will be from outside physician referrals.
- 4) Our ongoing multiple myeloma treatment study and outside physician referral network has a high representation of minorities.

2.2 SCREENING EVALUATION

2.2.1 Clinical evaluation must be completed within 4 weeks prior to study enrollment:

A complete history and physical examination with documentation of type of response (sCR, CR, VGPR, PR, MR or SD according to criteria described in section 6.2) to induction or re-induction treatment, the time interval from last treatment to documentation of response, and assessment of performance status using the ECOG scale must be performed prior to study entry. Patients will be evaluated for baseline neuropathy.

Abbreviated Title: Revlimid maintenance for MM

Version Date: 01/06/2017

2.2.2 The following studies and laboratory tests will be completed within 4 weeks prior to study entry:

- 2.2.2.1 CBC with differential
- 2.2.2.2 Reticulocyte count
- 2.2.2.3 Acute care panel, calculated creatinine clearance using Cockcroft-Gault formula (within 2 weeks prior to study entry)
- 2.2.2.4 Mineral panel, Hepatic panel, Uric acid, LDH, and Beta-2 Microglobulin
- 2.2.2.5 PT, PTT
- 2.2.2.6 Serum protein electrophoresis (SPEP) and immunofixation to assess for presence and quantity of monoclonal protein (M-protein)
- 2.2.2.7 Random urine sample for protein electrophoresis (UPEP) and immunofixation to assess for monoclonal protein in the urine (Bence-Jones proteinuria). Collect a 24 hour urine sample if necessary for confirmation of multiple myeloma response to prior (re)induction treatment, or if calculated creatinine clearance is <40 ml/min.
- 2.2.2.8 Serum free light chain studies
- 2.2.2.9 Quantitative immunoglobulins
- 2.2.2.10 Viral serologies:
 - Hepatitis B surface antigen
 - Anti Hepatitis C (HCV) antibody. If positive, will follow with HCV RNA PCR
 - HIV ELISA screening test. If positive, will follow with confirmatory Western Blot test
- 2.2.2.11 Review of bone marrow core biopsy or aspirate
- 2.2.2.12 Serum or urine pregnancy test in women of child-bearing potential (complete within 10-14 days and again within 24 hours prior to prescribing lenalidomide for cycle 1)
- 2.2.2.13 12-lead EKG
- 2.2.2.14 Skeletal survey of the axial and appendicular skeleton. Exception may be made if skeletal survey has been performed within the past 3 months and was found to be positive. In this case, films will be forwarded to the Clinical Center for confirmatory interpretation by the Department of Radiology.

2.3 REGISTRATION PROCEDURES

- 2.3.1 Authorized staff must register an eligible candidate with NCI Central Registration Office (CRO) within 24 hours of signing consent. A registration Eligibility Checklist from the web site (<http://home.ccr.cancer.gov/intra/eligibility/welcome.htm>) must be completed and faxed to [contact]. After confirmation of eligibility at Central Registration Office, CRO staff will call pharmacy to advise them of the acceptance of the patient on the protocol prior to the release of any investigational agents. Verification of Registration will be forwarded electronically via e-mail to the research team. A recorder is available during non-working hours.

Abbreviated Title: Revlimid maintenance for MM

Version Date: 01/06/2017

2.4 BASELINE EVALUATION

- 2.4.1 Research and clinical laboratory tests to be performed within 4 weeks of study entry and prior to starting therapy. Refer to section 5 for details on biospecimen collection and biomarker studies.
- 2.4.2 Peripheral Blood/Urine (see section 5)
 - 2.4.2.1 For storage and establishing a biobank (AppendixC in section [15](#))
 - 2.4.2.2 Flow cytometry and other assays (see section 5):
 - Phenotypic analysis of NK, NKT, and T cells
 - Phenotypic analysis of B cell subsets
 - Proliferation assays for human T cells (CD4 and CD8)
 - Functional NK cell analysis
 - Regulatory T cell and myeloid derived suppressor cell (MDSC) phenotype
 - Chemokine and cytokine assay
 - Selected tumor cell antigen targets
- 2.4.3 Bone Marrow (see section [5](#)). Bone marrow aspirate and biopsy will be used for histopathological evaluation, to determine the immunophenotyping of aberrant clonal plasma cells by multiparametric flowcytometry, CD 138+ and CD 138- fractions cell sorting with subsequent correlatives on both fractions, and the expression of CCRN by gene expression profiling and quantitative PCR.

3 STUDY IMPLEMENTATION

3.1 STUDY DESIGN

- Patients with newly diagnosed or relapsed MM with stable disease or better clinical response after induction or re-induction treatment will be enrolled on this phase II study and treated with a maintenance dose of lenalidomide 10 mg daily on days 1 to 21 of repeated 28-day cycles.
- Patients who complete at least 3 cycles will be evaluable for primary endpoints. Patients who do not complete three cycles of therapy will not be included in the analysis of primary or non-primary endpoints; and will be replaced by new patients.
- Using flow cytometry on peripheral blood, the four primary outcomes of T cell (CD4, CD8), NKT and NK cell numbers will be measured at pre-specified treatment time points to determine the difference in the counts of these parameters for each patient.

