- l. Patients removed from protocol therapy for unacceptable toxicities will be followed until resolution or stabilization of the adverse event. Further follow-up for patients taken off protocol therapy can be assessed either by phone consultation or clinic appointment at the discretion of the PI.
- m. Day 1 may be delayed for up to one week for Cycle 2 and beyond.

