3.5 CRITERIA FOR REMOVAL FROM PROTOCOL THERAPY AND OFF STUDY CRITERIA

3.5.1 Criteria for removal from protocol therapy

- 3.5.1.1 Patients with medically concerning grade 3 or 4 adverse events related to study drug may be taken off therapy at the discretion of the principal investigator.
- 3.5.1.2 Toxicity has not resolved after 8 weeks of withholding treatment
- 3.5.1.3 Grade 4 non-blistering rash, or blistering rash of any grade
- 3.5.1.4 Grade 4 neuropathy
- 3.5.1.5 Grade 4 hypersensitivity reaction
- 3.5.1.6 Progression of disease
- 3.5.1.7 Patient chooses to go off therapy
- 3.5.1.8 The principal investigator may remove patient from protocol therapy if deemed necessary due to medical conditions, compliance, etc.
- 3.5.1.9 Diagnosis of new malignancy
- 3.5.1.10 Patient becomes pregnant.

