3.5.2 Criteria for removal from study

- 3.5.2.1 Patient requests to be withdrawn from study
- 3.5.2.2 Death
- 3.5.2.3 Physician's determination that withdrawal is in the patient's best interest
- 3.5.2.4 Effective with amendment D, version date February 12, 2015, patients, will be removed from the study when they have completed two years of lenalidomide therapy and the 30 day safety follow-up visit. Patients who have on-going toxicity(ies) will be followed as described in Section **7.1.1**.

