6.2 RESPONSE CRITERIA

6.2.1 Response assessments will be performed on Day 1 (+/- 3 days) of cycles 2, 4 and 7; and on Day 1 (+/-3 days) of every third cycle starting at cycle 10 at scheduled clinic visits, at the time of documented CR, and at disease progression Disease Parameters

- Patients who have a measurable serum or urine M-protein. A "measurable" serum M-protein is ≥ 1 g/dL and a "measurable" urine M-spike is ≥ 200 mg/24 hours. If patient does not have a "measurable" serum or urine M-protein, but has either a serum kappa or lambda FREE light chain of 10 mg/dL along with an abnormal kappa to lambda free light chain ratio, patient is considered to have "measurable" disease.
- The serum free light chain (FLC) assay is of particular use in monitoring response to therapy in patients who have oligo-secretory disease. When using this assay, it is important to note that the FLC levels vary considerably with changes in renal function and do not solely represent monoclonal elevations. Thus both the level of the involved and the uninvolved FLC isotype (i.e., the involved/uninvolved ratio or involved-uninvolved difference) should be considered in assessing response. The serum FLC assay should be used in assessing response only if the baseline serum and/or urine M proteins are not "measurable" by traditional criteria (serum M protein ≥ 1 gm/dL and/or urine M protein ≥ 200 mg/24), and the baseline level of the involved FLC is 10mg/dL and clonal (abnormal ratio). Patients included on the study on the basis of FLC alone (i.e., no measurable serum/urine) should be the only ones who are evaluated using FLC response criteria. The others should follow usual criteria and ignore FLC results.
- In order to be classified as a hematologic response, confirmation of serum monoclonal protein, serum immunoglobulin free light chain (when primary determinant of response) and urine monoclonal protein (when primary determinant of response) results must be made by verification on two consecutive determinations.
- Caution must be exercised to avoid rating progression or relapse on the basis of variation of radiological technique alone. Compression fracture does not exclude continued response and may not indicate progression. When progression is based on skeletal disease alone, it should be discussed with the PI before removing the patient from the study.

6.2.2 Response Criteria from International Myeloma Workshop Consensus Panel Criteria⁴⁷:

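### The three-cycle evaluability rule also governs PFS, so progressions and deaths before the end of cycle 3 drop out of the Kaplan-Meier curve and bias it upward, probably by a small amount

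*Combined protocol and SAP*

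**What the plan says.** Section 3.1 makes patients evaluable for the primary endpoints once they complete three cycles. It then widens the rule: "Patients who do not complete three cycles of therapy will not be included in the analysis of primary or non-primary endpoints", and these patients are replaced.

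The other relevant provisions are:

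- Section 1.1.2 lists PFS first among the secondary objectives. Section 8.3 estimates PFS and duration of response by Kaplan-Meier and names no analysis set or landmark.
- PFS runs from start of treatment in Section 6.2.4 and from study entry in Section 8.3. Both precede the end of cycle 3.
- The criteria for ending protocol therapy include "3.5.1.6 Progression of disease".
- On disease assessment, Section 6.2.1 says: "Response assessments will be performed on Day 1 (+/- 3 days) of cycles 2, 4 and 7", and then every third cycle from cycle 10.
- On timing, Section 3.4 says: "Day 1 may be delayed for up to one week for Cycle 2 and beyond". A dose hold can stretch a cycle further; removal follows only when "Toxicity has not resolved after 8 weeks of withholding treatment".
- Under Section 3.5.2 patients are "removed from the study when they have completed two years of lenalidomide therapy" and the 30-day safety visit.

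**The concern.** The paired tests compare baseline with the post-cycle-3 sample, so a patient without that sample cannot contribute. PFS needs no such sample. Applying the same rule to PFS makes inclusion depend on the outcome, because an early progression or death is itself a reason for not completing three cycles. Retained patients are counted as at risk from time zero although they had to survive progression-free on therapy to the end of cycle 3 to be counted at all. Replacement then refills the sample with patients who passed the same filter, so the final number shows no loss.

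At stake is a systematic error of known sign in the first secondary endpoint, one that its confidence interval would not reveal. The rule also removes patients who stop for toxicity or by choice; the documents do not determine the direction of any bias from that part.

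Duration of response is affected only conditionally. A response "must be made by verification on two consecutive determinations", and the first two scheduled assessments are C2D1 and C4D1, so scheduled visits cannot confirm a new response before cycle 3 is complete. Early loss matters only if a response confirmed on unscheduled tests, or one carried in from induction and noted at screening ("documentation of type of response (sCR, CR, VGPR, PR, MR or SD according to criteria described in section 6.2"), counts.

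**Working it through.** **The plan's own figures.** The plan states no figure for PFS. Its one design figure, 80% power for the paired t-test (n = 28, 0.67 SD, two-sided 0.013), reproduces at 80.4% by the noncentral t distribution. It does not involve PFS and this point leaves it untouched.

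**Step 1: no assumption about PFS.** Let 28 evaluable patients be kept and k be lost to early progression or death. All 28 are event-free through cycle 3, so the reported curve is 1 there. With the k events restored it would be 28/(28+k). Later conditional steps are unchanged, so every later reported value is too high by the factor (28+k)/28.

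| k | factor | a reported 0.60 would be |
|---|---|---|
| 1 | 29/28 = 1.036 | 0.579 |
| 2 | 30/28 = 1.071 | 0.560 |
| 3 | 31/28 = 1.107 | 0.542 |

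**Step 2: how large k might be.** This needs assumptions. Inputs:

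- Median PFS of 31 months: the lowest lenalidomide-maintenance arm in Table 1 (Section 1.2).
- Survival S(t) = exp(−ln2 × (t/median)^shape); shape 1 is exponential. One month is 30.44 days.
- Cut-off c. Day 28 loses only events up to C2D1. Day 84 (3 × 28) loses every event during three on-schedule cycles. Day 98 (84 + 7 + 7) applies if C2D1 and C3D1 are each delayed by the permitted week; dose holds could extend it further.
- Only PFS events cause loss; toxicity and voluntary withdrawal are not modelled.

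Formulas: fraction dropped p = 1 − S(c); replaced per 28 kept = 28p/(1−p); reported curve S′(t) = S(t)/S(c).

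Example, exponential, day 84: c = 84/30.44 = 2.76 months; S(c) = exp(−0.693 × 2.76/31) = 0.940; p = 0.060; replaced = 28 × 0.060/0.940 ≈ 1.8; S′(24) = 0.585/0.940 = 0.622.

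| Median, shape | Cut-off day | Dropped | Replaced | 12-month PFS, true → reported | 24-month PFS, true → reported |
|---|---|---|---|---|---|
| 31, 1 | 28 | 2.0% | 0.58 | 0.765 → 0.781 | 0.585 → 0.597 |
| 31, 1 | 84 | 6.0% | 1.78 | 0.765 → 0.813 | 0.585 → 0.622 |
| 31, 1 | 98 | 7% | 2.09 | 0.765 → 0.822 | 0.585 → 0.628 |
| 31, 1.5 (low early hazard) | 28 / 84 | 0.4% / 1.8% | 0.10 / 0.52 | 0.846 → 0.849 / 0.862 | 0.624 → 0.626 / 0.635 |
| 31, 0.75 (high early hazard) | 28 / 84 | 4.8% / 10.7% | 1.42 / 3.35 | 0.712 → 0.748 / 0.797 | 0.564 → 0.593 / 0.632 |
| 13, 1 (lowest Table 1 arm, placebo) | 28 / 84 | 4.8% / 13.7% | 1.41 / 4.44 | 0.527 → 0.554 / 0.611 | 0.278 → 0.292 / 0.322 |

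**Step 3: against sampling error.** SE = √(S(1−S)/28). For the 31-month exponential case this is √(0.765 × 0.235/28) = 0.080 at 12 months and √(0.585 × 0.415/28) = 0.093 at 24 months. The on-schedule shifts, from unrounded values, are 0.016 to 0.049 at 12 months and 0.012 to 0.037 at 24 months, all below one SE. At a 13-month median, day 84, the 12-month shift of 0.084 comes close to its SE of 0.094.

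**Median.** No shift is quoted for the base case. Patients leave the study at about 25 months, when S is still about 0.57. Section 8.1 lists reasons for stopping without the two-year limit, but Sections 3.2 and 3.5.2.4 set it.

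**The case against.** The strongest reply is that little turns on this. PFS has no test, precision target or decision rule, Section 8.1 promises descriptive results, and the exclusion is stated openly, so a reader could take the curve as describing patients who completed three cycles. The lack of a decision rule stands and limits the severity. The labelling argument does not: Sections 6.2.4 and 8.3 define PFS from the start of treatment or study entry, and nothing in 8.3 presents it as a landmark analysis.

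A second reply, pointing the other way, is that the documents do not establish a small bias. The 31-month arm comes from a trial whose cited title says newly diagnosed myeloma, whereas this trial also enrols relapsed patients in an unstated mix. This is fair. With assumed mixtures (relapsed median 6 to 18 months, relapsed share 25% to 75%, the rest at 31 months, day 84) the 24-month shift is 4.1 to 6.5 points.

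Third, no disease assessment is scheduled between C2D1 and C4D1. Many progressions arising in cycles 2 and 3 would first be found at C4D1, after three completed cycles, and would stay in. This also stands and points toward the day-28 end of each range. It is not airtight: completing three cycles is not defined, and C4D1 tests may be done up to three days early, so a progression found then could be classified either way.

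Finally, the factor (28+k)/28 is conditional. If t patients who stopped for other reasons are restored as censored after the k events, it becomes (28+k+t)/(28+t); for k = 2 and t = 3 that is 33/31 = 1.065 rather than 1.071. The difference is minor.

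**Conclusion.** The concern holds. As written, the plan removes from PFS the progressions and deaths that prevent completion of cycle 3, and for that part the reported curve can only be too high. The direction follows from the text and needs no assumption.

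The size is an inference. With a 31-month exponential median and on-schedule cycles, 24-month PFS is overstated by about 1 to 4 percentage points and 12-month PFS by about 2 to 5, below one standard error with 28 patients. The assessment schedule favours the lower end. A predominantly relapsed population or a high early hazard would push it up: 24-month shifts of 3 to 7 points at shape 0.75, and a 12-month shift of about 8 points at a 13-month median if all events to day 84 are lost. Small is therefore likely, not guaranteed.

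This should be corrected but does not threaten the trial's main conclusion, because the four paired cell-count tests are unaffected.

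**What to change.** - **Section 3.1:** limit the three-cycle evaluability and replacement rule to the four paired cell-count comparisons and other paired biomarker changes.
- **Section 8.3:** analyse PFS in all patients who receive at least one dose of lenalidomide, including those later replaced. Censor patients who stop without progression or death at their last disease assessment.
- **Sections 6.2.4 and 8.3:** use one time origin for PFS.
- **Duration of response:** analyse all treated responders, including those replaced, and state whether a response carried in from induction counts.
- **Reporting:** give the number replaced, by reason (progression, death, toxicity, choice).

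The cost is a wording change with no extra patients or visits. Reported PFS becomes slightly less favourable. Some patients who stop early for toxicity will be censored early, because the off-treatment data listed in Section 6.1 cover adverse events, survival status and further therapy, but not progression.
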